## 4. DEFINITIONS

### 4.1. Time-Related Terms

#### 4.1.1. Baseline Visit

The *Baseline Visit* is Visit 2 (Day 1) when the subject is randomized.

#### 4.1.2. Treatment Start Date and Treatment End Date

*Treatment start date* and *treatment end date* for each treatment period are defined as follows in [Table 3](#).

**Table 3: Definitions for Treatment Start and End Dates by Treatment Period**

| Treatment Period                    | Treatment Start Date   | Treatment End Date   |
|-------------------------------------|--|--|
| Double-Masked (DM) Treatment Period | The date at which a randomized subject takes the first dose of the DM study drug       | 
The date at which a randomized subject takes the last dose of the DM study drug. If the date of the last dose is missing and the subject does not receive any OL study drug:
 
 
• The day before the Visit 5 (Month 3) date will be considered the treatment end date for subjects who completed the Month 3 Visit
 
• The day before the Exit Visit date will be used for subjects who prematurely discontinued from the study before Visit 5 (Month 3). If the Exit Visit date of a non-completer is not available, then the day before the last available visit date will be considered the treatment end date
 
 |
| Open-Label (OL) Treatment Period    | The date at which a randomized adult subject takes the first dose of the OL study drug | 
The date at which a randomized adult subject takes the last dose of the OL study drug. If the date of the last dose is missing:
 
 
• The day before the Visit 8 (Month 12) date will be considered the treatment end date for subjects who completed the Month 12 Visit
 
• The day before the Exit Visit date will be used for subjects who prematurely discontinued from the study during OL period. If the Exit Visit date of a non-completer is not available, then the day before the last available visit date will be considered the treatment end date
 
  |

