21. Presence or history of any disease or condition that, in the opinion of the study Investigator, may put the subject at significant risk (such as contraindication to the use of Timolol Maleate Ophthalmic Solution 0.5%), may confound study results, or may interfere significantly with the subject's participation in the study (e.g., recurrent corneal erosion syndrome, uncontrolled cardiovascular disease etc.).
22. Any decision by the Investigator or Medical Monitor to terminate a subject in screening or declare any subject ineligible for any sound medical reason.

Investigational product, dosage and mode of administration:

Subjects will be assigned in a 1:1 ratio to the DE-117/Vehicle arm and Timolol Maleate arms as follows:

Investigational Product:

DE-117 Ophthalmic Solution contains 0.002% DE-117. Each 2.5 mL bottle of DE-117 Ophthalmic Solution 0.002% contains 50 µg of DE-117. In addition,

Vehicle:

The vehicle is the same as the vehicle used in DE-117. [REDACTED]

Comparator:

Timolol Maleate Ophthalmic Solution 0.5% contains the active ingredient, timolol 5 mg/mL and the preservative BAK 0.01%. Other ingredients include monobasic and dibasic sodium phosphate and purified water. The pH is adjusted to 6.5 to 7.5 with sodium hydroxide.

During the Double-Masked Treatment Period subjects will be instructed to instill one drop of study medication from bottle labeled “evening” in each eye at 20:00 and one drop of study medication from bottle labeled “morning” in each eye at 08:00 starting in the evening of Visit 2 (Baseline, Day 1) through the morning before Visit 5 (Month 3). After the Visit 5 (Month 3), adult subjects will be instructed to instill one drop of study medication from bottle labeled “evening” in each eye at 20:00 through the morning before Visit 8 (Month 12). Note: Open-label DE-117 Ophthalmic Solution 0.002% will be dispensed at Visits 6 and 7.

Route of Administration of Investigational Product: Topical ocular**Duration of the Study:**

Adult subjects: The study duration includes up to 5 weeks Screening Period, a 3-month Double-Masked Treatment Period, and a 9-month Open-Label Treatment Period.

Pediatric subjects: The study duration includes up to 5 weeks Screening Period and a 3-month Double-Masked Treatment Period.

Criteria for Evaluation:**Efficacy:**

Efficacy will be assessed by evaluating IOP at scheduled time points (08:00, 10:00 and 16:00) at all scheduled visits with the exception of the Screening visit.

Safety:

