7.4.5. Visit 4 (Week 6, Day 43 ± 3)

- Update concomitant medications and procedures/therapies.
- An authorized unmasked study staff member, other than the Investigator or Examiner should query the subject regarding dosing compliance.
- Query the subject regarding AEs.
- As per Schedule of Events and Procedures [Table 3](#) (for adult subjects) **or** [Table 4](#) (**for pediatric subjects**), perform the following procedures or assessments immediately before the 08:00 IOP measurement (all ophthalmic procedures to be performed in both eyes):
 - BCVA (before the 08:00 IOP measurement)
 - If more than 10 letters in BCVA were lost compared to the screening visit, then refraction should be performed again.
 - Biomicroscopy (before the 08:00 IOP measurement)
- Perform IOP measurement at 08:00 (± 60 min).
- Instill study medication/eye drop after the 08:00 IOP measurement in both eyes (**for pediatric subjects, the investigator may elect to dose only one eye, the study eye**). An authorized unmasked study staff should make sure the instillation is performed.
- Perform IOP measurement at 10:00, and 16:00 (± 60 min).

- An authorized unmasked study staff member, other than the Investigator or Examiner, must:
 - Collect all used and unused bottles of study medication.
 - Dispense the assigned kit (from BALANCE) to the subject which will contain the following;
 - Two (2) bottles of study drug labeled “morning”
 - Two (2) bottles of study drug labeled “evening”
 - Instruct the subject not to show or discuss their study medication with other study staff including the Investigator or Examiner, or other study subjects.
- If the subject provided written consent to provide a blood sample for a future pharmacogenomics/genomics laboratory research study, the sample may be collected at this visit or subsequent visit prior to exit from the study, if not collected at the previous visit.
- Schedule the subject to return on Day 91±7 for Visit 5 (Month 3).
- Remind the subject to continue dosing according to the written instructions.
- Inform the subjects they will be reminded of the evening instillation of the study medication by phone call a few days before Visit 5.
- Remind the subjects that the morning dose of Visit 5 will be done at the clinic.
- Remind the subject to bring all used and unused study medication at Visit 5.

7.4.6. **Visit 5 (Month 3, Day 91 ±7)**

- Update concomitant medications and procedures/therapies.

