- An authorized unmasked study staff member, other than the Investigator or Examiner should query the subject regarding dosing compliance.
- Query the subject regarding AEs.
- Perform vital signs (blood pressure/pulse rate) measurements at approximately 08:00.
- As per Schedule of Events and Procedures [Table 3](#) (for adult subjects) **or** [Table 4](#) (**for pediatric subjects**), perform the following procedures or assessments immediately before the 08:00 IOP measurement (all ophthalmic procedures to be performed in both eyes):
 - BCVA (before the 08:00 IOP measurement)
 - If more than 10 letters in BCVA were lost compared to the screening visit, then refraction should be performed again.
 - Biomicroscopy (before the 08:00 IOP measurement)
- Perform IOP measurement at 08:00 (±60 min).

- Instill study medication/eye drop after the 08:00 IOP measurement in both eyes (**for pediatric subjects, the investigator may elect to dose only one eye, the study eye**). An authorized unmasked study staff should make sure the instillation is performed.
- Perform IOP measurement at 10:00 and 16:00 (± 60 min).
- Perform ophthalmoscopy in both eyes immediately after the 16:00 IOP measurement.
- As per Schedule of Events and Procedures [Table 3](#) (for adult subjects) **or** [Table 4](#) (**for pediatric subjects**), perform the following procedures or assessments at any time during this visit.
 - Assess any changes from baseline in Iris color, Eyelash, Eyelid and take front view and side view photographs of each eye. The following six (6) photos are required at this visit as follows:

- Obtain urine and perform urine pregnancy test, if the subject is a female of child-bearing potential.
- An authorized unmasked study staff member, other than the Investigator or Examiner, must:
 - Collect all used and unused bottles of study medication.

Note:

- **If the study drug administration is discontinued prior to Visit 5, the subject should be encouraged to still participate in follow-up study visits until Visit 5 on an observational basis.**
- **If the study drug administration is discontinued prior to Visit 5, then to the extent possible, all procedures for Study Exit/Early Termination as per [Table 3](#) (for adult subjects) **or** [Table 4](#) (**for pediatric subjects**) will be performed on the day of early termination. Subjects who are discontinued from the study early will not be replaced.**

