8.5. Subject Withdrawal Criteria

An early termination occurs when a subject who provides written informed consent ceases participation in the study, regardless of circumstances, before the completion of the study. Subjects may be voluntarily discontinued from study medication or withdrawn from the study at any time for any reason. In addition, the Principal Investigator or Medical Monitor may discontinue the study drug administration or terminate a subject's study participation due to any of the following reasons:

- AE (e.g., not compatible with study continuation)
- Non-compliance with study drug
- Lack of efficacy (e.g., IOP exceeds 34 mmHg in either eye after randomization)
- Progressive disease

- Protocol deviation (e.g., not fulfilling eligibility criteria)
- Pregnancy
- Voluntary withdrawal by subject at any time for any reason
- Lost to follow-up (e.g., no contact is possible)
- Death
- Other

If the study drug administration is discontinued prior to Visit 5, they should be encouraged to still participate in follow-up study visits until Visit 5 on an observational basis.

[figure not shown]
If the study drug administration is discontinued prior to Visit 5, then to the extent possible, all procedures for Early Termination will be performed on the day of early drug discontinuation as per [Table 3](#) (for adult subjects) or [Table 4](#) (for pediatric subjects). Subjects who are discontinued from the study early will not be replaced.

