## 7. SUMMARY OF STUDY POPULATION DATA

### 7.1. Subject Disposition

The disposition of ITT population (i.e., all randomized subjects) will be summarized by treatment period (double-masked and open-label) and by planned treatment (for double-masked period) and overall.

For the double-masked period, the summary will include the number and percentage of ITT subjects in the Safety population, FAS, and PPS. The disposition summary will also include the number and percentage of subjects who completed the study drug, subjects who discontinued the study drug prematurely but continued with study participation until the Month 3 Visit and among which who completed or not completed the Month 3 Visit, as well as the number and percentage of subjects who discontinued from the study or discontinued from the study drug prior to Month 3 Visit by the primary discontinuation reason.

For the open-label period, the summary will include the number and percentage of subjects who received any study treatment during open-label period, and subjects who are still on the study at the time of data cut (for reports other than the final clinical study report). The disposition summary will also include the number and percentage of subjects who completed the study drug, and subjects who discontinued from the study prior to Month 12 Visit by the primary discontinuation reason.

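### Where the last masked-dose date is missing and no open-label drug was taken, SAP Table 3 dates the end of treatment from Month 3 attendance, whenever the drug was actually stopped

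*SAP*

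**What the plan says.** SAP Table 3 (section 4.1.2) defines the masked treatment end date as the date of the last masked dose. A fallback follows, with a two-part trigger: "If the date of the last dose is missing and the subject does not receive any OL study drug". Under that trigger there are two rules. For Month 3 attenders: "The day before the Visit 5 (Month 3) date will be considered the treatment end date for subjects who completed the Month 3 Visit". For those who left the study earlier: "The day before the Exit Visit date will be used for subjects who prematurely discontinued from the study before Visit 5 (Month 3".

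Protocol 8.5 says of subjects whose drug is stopped before Visit 5 that "they should be encouraged to still participate in follow-up study visits until Visit 5 on an observational basis", and SAP 3.4 repeats this. SAP 7.1 gives them their own disposition line: "subjects who discontinued the study drug prematurely but continued with study participation until the Month 3 Visit". Protocol 8.5 also asks that the early-termination procedures be done, as far as possible, on the day the drug is stopped.

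The end date feeds three definitions: duration of exposure (SAP 4.1.5, summarised in 7.7), the treatment-emergent window, which closes two days after treatment ends (4.4.1), and concomitant-medication status, which needs overlap with the study-drug period (4.5.1).

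**The concern.** A subject who stops drug in week 3 and keeps attending has completed the Month 3 visit. If the last-dose date is missing and no open-label drug is taken, the attender rule applies and treats the whole of follow-up as treatment. The second rule does not rescue this case, because it is written for people who left the study and this subject did not.

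Three things would then go wrong in the safety reporting. Exposure would be too long. Adverse events arising weeks after the last drop would enter the treatment-emergent tables, which under SAP 4.4.1 are the only adverse-event tables produced. Therapy started after stopping would be classed as concomitant with study drug. The error need not be balanced between arms: SAP 8.1.1.2 itself provides an extra analysis in case discontinuation for lack of efficacy or adverse events differs between them.

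**Working it through.** The plan states no figure that depends on this rule, so the check is date arithmetic on its own definitions.

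**Inputs**
- First dose on Day 1 (Protocol 7.4.3; study-day convention in SAP 4.1.3).
- Visit 5 on Day 91, window Day 84 to 98 (SAP Table 4).
- Exposure = end date − start date + 1 (SAP 4.1.5).
- Treatment-emergent window closes at end date + 2 days (SAP 4.4.1).
- Masked-period exposure categories 1-30, 31-60 and ≥61 days (SAP 7.7).
- The early last-dose days below are illustrations; the documents give none.

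**Rule.** Imputed end = 91 − 1 = Day 90. Exposure = 90 − 1 + 1 = 90 days. Window closes on Day 90 + 2 = Day 92.

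| Actual last dose | Exposure, rule / actual | Excess days | Category, rule / actual | Window closes, rule / actual |
|---|---|---|---|---|
| Day 1 | 90 / 1 | 89 | ≥61 / 1-30 | Day 92 / 3 |
| Day 20 | 90 / 20 | 70 | ≥61 / 1-30 | Day 92 / 22 |
| Day 45 | 90 / 45 | 45 | ≥61 / 31-60 | Day 92 / 47 |
| Day 60 | 90 / 60 | 30 | ≥61 / 31-60 | Day 92 / 62 |
| Day 91 (in clinic) | 90 / 91 | −1 | ≥61 / ≥61 | Day 92 / 93 |

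For the Day 20 case, exposure is overstated 90/20 = 4.5 times, and the window is 92 − 22 = 70 days too long. The largest possible excess, for a last dose on Day 1, is (84 − 1) − 1 = 82 days to (98 − 1) − 1 = 96 days across the Visit 5 window.

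**Who can be reached.** SAP 3.1 plans for all adults (about 400) to go on to open-label drug, which takes them outside the trigger. What remains is anyone with a missing date among up to 30 children, plus adults who take no open-label drug.

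**The last row.** It depends on whether a masked dose is taken on the Visit 5 date, and the protocol is not consistent. The synopsis has masked dosing run "through the morning before Visit 5 (Month 3". Section 7.4.5 instructs staff: "Remind the subjects that the morning dose of Visit 5 will be done at the clinic". The Visit 5 procedures in 7.4.6 use the same wording as Visits 3 and 4: "Instill study medication/eye drop after the 08:00 IOP measurement in both eyes". The compliance denominator in SAP 7.6 matches the in-clinic reading. Summed to Day 91 it is 2 × 90 = 180 doses, which equals 1 (evening of Day 1) + 89 × 2 = 178 (Days 2 to 90) + 1 (morning of Day 91).

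**The case against.** The strongest objection is scope. A reader might infer that the SAP ends masked treatment the day before Visit 5 for everyone who attends Month 3. It does not: the recorded date comes first, and the fallback also requires that no open-label drug was taken. That objection stands in full and limits the point.

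Second, the case is remote. It needs an early stop, attendance at Visit 5, no open-label drug and a missing date all together. Early-termination procedures are due on the day of stopping, and unmasked staff ask about dosing at Visits 3, 4 and 5, so the date should often exist. Nothing in the documents bars an adult who stopped early from the open label. This bears on frequency. It does not make the rule right when it applies.

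Third, a reader might infer that exposure is systematically wrong for completers. At most it is one day, the category does not change, the protocol passages conflict, and in the DE-117 arm the 08:00 drop is vehicle. Children also exit at Visit 5, where adverse-event recording ends (Protocol 12.1.1.2), so a one-day shift in their window has almost no effect.

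Fourth, a reader might call the Exit Visit rule wrong for people who stop drug, stay a while and then leave. That depends on what Exit Visit means. SAP 3.4 ties it to leaving the study. Protocol 8.5 puts the early-termination procedures on the day drug is stopped, and the schedules share one column for exit and early termination. The term is ambiguous, so an error is not established.

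Finally, an over-long window counts more events, which is usually the cautious direction, and SAP section 6 plans no safety testing. That stands in part, but overstated exposure is not cautious, and extra events in the timolol arm would not be cautious for DE-117.

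**Conclusion.** The point holds in limited form. For subjects with a missing masked last-dose date and no open-label drug, Table 3 imputes the end of treatment from attendance at Month 3, and this is wrong for those who stopped early and stayed, a group the plan itself recognises. The error for one such subject can reach 89 days with Visit 5 on Day 91 (96 at the late edge of the window). It moves exposure from a lower category to ≥61 and brings off-drug events and therapies into the on-treatment tables. How many subjects are affected is unknown and probably few. The conclusion assumes that some early stoppers do not enter the open label, which the documents neither state nor exclude.

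A reader might infer an effect on the efficacy results. The SAP does not support that: censoring in 6.2.1 and section 8 is keyed to receipt of other IOP-lowering therapy, not to the treatment end date. This is a worthwhile wording correction for the safety tables and no more.

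**What to change.** In the masked-period row of Table 3, tie the fallback to drug status:
- **Drug stopped before Visit 5:** use the date of the early-termination procedures, or a recorded drug-discontinuation date if one is collected. The documents do not show such a field, and the procedures are required only as far as possible, so the SAP should also say what is used if neither date exists.
- **Exit Visit:** define the term, and use the day before it only when drug and study were stopped together.
- **Still on drug at Visit 5:** first reconcile the synopsis with Protocol 7.4.5 and 7.4.6 on whether a masked dose is taken that day. If the in-clinic dose is confirmed, use the Visit 5 date. This is a one-day, minor point.

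The same edit could cover adults who do enter the open label with a missing masked date. Table 3 gives them no fallback, although SAP 7.7 subtracts days on timolol to obtain DE-117 exposure.

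The cost is minor SAP wording and programming work.

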Final eligibility for randomization will be determined at Visit 2 (Baseline) after all necessary washouts from prior IOP-lowering medications have been completed. Subjects who have not used any IOP-lowering medication for the last 28 days, including treatment-naive subjects, must have ≥ 1 day between their screening visit and Visit 2 (Baseline).

At Visit 2, baseline IOP will be measured for both eyes at 08:00 (± 60 min), 10:00 (± 60 min) and 16:00 (± 60 min). The study eye will be the eye that qualifies per eligibility criteria at Visit 2. If both eyes meet the eligibility criteria, the eye with the higher mean diurnal IOP at Visit 2 will be designated as the study eye. If both eyes meet the eligibility criteria and have the same mean diurnal IOP, the right eye will be designated as the study eye. Both eyes should be treated with the study medication for the duration of the study, even if only one eye is eligible per IOP inclusion criteria. **For pediatric subjects, if only one eye has a diagnosis of glaucoma or OHT, the fellow eye doesn't have to be treated by the study medications for the duration of the study.**

Double-Masked Treatment Period (3 months, for all subjects):

Approximately 400 eligible adult subjects and up to 30 pediatric subjects will be randomized to receive either DE-117 0.002% QD in the evening and vehicle QD in the morning or Timolol Maleate 0.5% BID in a 1:1 ratio. Subjects will be treated for 3 months with scheduled visits at Visits 2, 3, 4 and 5 (Baseline, Week 1, Week 6 and Month 3).

At Visit 2 (Baseline), subjects will receive their first dose of study medication (study eye drops) as per their assigned/randomized study treatment at 20:00 (± 60 min). The next day, subjects will subsequently dose with their assigned study medication at 08:00 (± 60 min), and 20:00 (± 60 min). At each scheduled follow-up visit, subjects will receive their morning dose of study medication/eye drops following the 08:00 IOP measurement at the investigative site (the doctor's office).

Timolol Maleate Ophthalmic Solution 0.5% was chosen as the active control because it has previously been proven to be effective for the reduction of elevated IOP in patients with glaucoma or OHT and is approved for these indications.

Open-Label Treatment Period (9 months, for adult subjects only):

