**Table 3: Definitions for Treatment Start and End Dates by Treatment Period (Continued)**

| Treatment Period | Treatment Start Date   | Treatment End Date   |
|------------------|--|--|
| Entire Study     | The date at which a randomized subject takes the first dose of the DM study drug | The date at which a randomized subject takes the last dose of the study drug.
Missing last dose date will be handled the same way as mentioned above. |

Notes:

1. Pediatric subjects only participate in the double-masked period.
2. For each treatment period, the treatment end date will be set to missing if the treatment start date is missing.

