#### 4.1.3. Study Day

The *study day* describes the relative day of an observation starting with the reference date designated as Study Day 1. In this study, the treatment start date is the reference date. Thus, the study day will be calculated as:

- For days prior to the treatment start date, Study Day = Date – Treatment Start Date
- For days on/after the treatment start date, Study Day = Date – Treatment Start Date + 1

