#### 4.1.4. Out-of-Window Measurements, Analysis Visit, and Analysis Window

*Analysis visit* is a timing variable to be used for analyses involving visits. For each analysis visit, an *analysis window* is set up to determine the analysis visit to which a measurement should be mapped (Table 4).

The analysis visit of a measurement will be determined based on the study day of the measurement and specified analysis windows and is not necessarily the same as the study visit at which the measurement was collected. For example, an out-of-window measurement collected at the Week 1 study visit will be mapped to the Week 6 analysis visit, if the study day of the measurement falls into the analysis window of Week 6.

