## 4.4. Safety-Related Definitions

### 4.4.1. Adverse Event

Under Protocol 011709IN, an AE is defined as any untoward medical occurrence that occurs in a study subject, regardless of the causal relationship with the study treatment. An *on-study* AE can occur any time after the date of informed consent through the last study visit. An AE will be considered as *treatment-emergent* if the onset date of the AE occurred on or after the treatment start date till up to 2 days (twice the scheduled dosing interval) after treatment end date.

Treatment-emergent AEs (TEAEs) are a subset of on-study AEs. Both on-study and TEAEs will be collected, but only TEAEs will be tabulated.

The severity of each AE will be graded by the Clinical Investigator as Mild, Moderate, or Severe. AEs will also be rated by the Investigator as to their causality/relationship to the study drug.

Each AE will be classified into a system organ class (SOC) and coded to a preferred term (PT) using Medical Dictionary for Regulatory Activities (MedDRA), Version 21.1 published in 2018.

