## 7.7. Exposure to Study Medication

The duration of exposure to a study medication is measured by days on treatment as derived in [Section 4.1.5](#). For subjects in the Safety Population, the duration of exposure will be summarized using descriptive statistics, and frequency and percentage of subjects will be tabulated by actual treatment received for double masked period and for the entire study separately. For the entire study period, the duration of exposure to overall DE-117 treatment will also be provided, which will combine exposure to DE-117 from both double-masked arms. For subjects who were in the Timolol arm during double-masked treatment period, their duration of exposure to DE-117 will be the total duration on the study minus the number of days they were exposed to Timolol treatment.

The duration of exposure categories are:

- Double-masked period: 1-30, 31-60, or  $\geq 61$  days
- Entire study period: 1-30, 31-60, 61-90, 91-120, 121-150, 151-180, 181-210, 211-240, 241-270, 271-300, 301-330, or  $\geq 331$  days

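### SAP Table 3 misdates treatment in two narrow cases: a non-completer with neither an Exit Visit nor a last-dose date, and a dosed subject with no first-dose date

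*SAP*

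**What the plan says.** SAP Table 3 defines the double-masked start date as "The date at which a randomized subject takes the first dose of the DM study drug". The end date is the date of the last dose. If that is missing (and, in the double-masked row, no open-label drug was received), a fallback applies. Completers get the day before Visit 5 or Visit 8, and non-completers get the day before the Exit Visit. For a non-completer without an Exit Visit, the end of treatment is set thus: "If the Exit Visit date of a non-completer is not available, then the day before the last available visit date will be considered", and the open-label row repeats this rule.

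Note 2 to the table adds: "For each treatment period, the treatment end date will be set to missing if the treatment start date is missing". Neither Table 3 nor SAP Table 7, which covers only medical history, adverse event and concomitant medication dates, imputes a missing first-dose date.

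Three derivations depend on these dates:
- Exposure (SAP 4.1.5) uses both dates.
- The treatment-emergent window (SAP 4.4.1) runs from the start date "till up to 2 days (twice the scheduled dosing interval) after treatment end date".
- Study day (SAP 4.1.3) uses the start date alone: "In this study, the treatment start date is the reference date". SAP 4.1.4 then assigns visits from study day: "The analysis visit of a measurement will be determined based on the study day of the measurement and specified analysis windows".

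**The concern.** The day-before rule suits a visit at which treatment has already stopped. It does not suit the visit at which dosing starts, nor one in mid-treatment. Protocol 7.1 schedules the first double-masked dose for 20:00 on Visit 2 and the first open-label dose for the evening of Visit 5, so the day before either visit precedes treatment in that period. At Visits 3 and 4 a dose is given on site: "At each scheduled follow-up visit, subjects will receive their morning dose of study medication/eye drops following the 08:00 IOP measurement". Protocol 7.4.4 and 7.4.5 have unmasked staff make sure that it is instilled, so the rule ends treatment the day before a supervised dose.

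Note 2 makes sense for a subject who was never dosed, or who never entered open label. It does not separate that subject from one who was dosed on an unrecorded date. The dosed subject stays in the Safety Population and, with baseline and post-baseline IOP, in the FAS, yet none of the time-based derivations can be made.

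At stake are the exposure table for early losses and, in the second case, all of a treated subject's mapped efficacy data.

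**Working it through.** The SAP gives no worked figure to reproduce. The check is date arithmetic with its own rules.

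Inputs:
- Start: Day 1 (Visit 2) for double-masked; the Visit 5 date, nominally Day 91, for open label (Protocol 7.1).
- Nominal visit days: 8, 43 and 91 (SAP Table 4).
- Fallback end = last available visit − 1 (SAP Table 3).
- Exposure = end − start + 1 (SAP 4.1.5).
- Last treatment-emergent day = end + 2 (SAP 4.4.1).

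Day 0 below means the calendar day before Day 1.

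**Case (a): no last-dose date, no Exit Visit**

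| Last visit | Start | Fallback end | Exposure | Exposure if end = visit day | Last treatment-emergent day |
|---|---|---|---|---|---|
| Visit 2 (Day 1) | 1 | 0 | 0 − 1 + 1 = 0 | 1 | 0 + 2 = Day 2 |
| Visit 3 (Day 8) | 1 | 7 | 7 − 1 + 1 = 7 | 8 | 7 + 2 = Day 9 |
| Visit 4 (Day 43) | 1 | 42 | 42 − 1 + 1 = 42 | 43 | 42 + 2 = Day 44 |
| Visit 5 (Day 91), open label | 91 | 90 | 90 − 91 + 1 = 0 | 1 | 90 + 2 = Day 92 |

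If the last visit is Visit 2 but the first dose is recorded on Day 2, exposure is 0 − 2 + 1 = −1.

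*Exposure categories.* SAP 7.7 uses "Double-masked period: 1-30, 31-60, or" 61 days and over, so 0 has no category. The one-day shortfall at Visits 3 and 4 changes no category within the protocol windows: Days 6 to 10 give 5 to 9 days, and Days 40 to 46 give 39 to 45.

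*Open label.* SAP 7.7 tabulates the double-masked and entire-study periods. For a subject last seen at Visit 5, entire-study exposure is still 90 − 1 + 1 = 90 days. What is affected is the DE-117 exposure of former timolol-arm subjects, which is total duration minus timolol days. Taking total duration as those 90 days, it is 90 − 90 = 0 if timolol is dated to Day 90, or 90 − 91 = −1 if the Visit 5 morning dose is dated to Day 91.

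*Adverse events.* SAP 4.4.1 ends on-study events at the last study visit and makes treatment-emergent events a subset of them. The window ends at (last visit − 1) + 2 = last visit + 1, which is later in every row. No on-study event is lost.

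*Study day and efficacy.* Study day needs only the start date, so it is unaffected. A subject last seen at Visit 2 has no post-baseline IOP and is outside the FAS anyway.

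**Case (b): first-dose date missing in a dosed subject**

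1. The end date is set to missing, even if it was recorded (Note 2).
2. Exposure and the treatment-emergent window cannot be derived. Only adverse events with a completely missing onset date still count as treatment-emergent (SAP Table 7).
3. There is no study day, hence no analysis visit (SAP 4.1.3, 4.1.4).
4. The MMRM in SAP 8.1.1.1.1 has analysis visit as a factor, so the subject's values at all nine primary timepoints have no place in it.

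**The case against.** The strongest case against is that little follows from either gap.

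- **Inversion is rare.** It needs a dosed subject, a missing last-dose date, no Exit Visit and no visit after the one at which dosing began. That is correct. A reader might infer that subjects lost to follow-up in general get zero exposure or lose their study days. The documents do not support this: losses after Visit 3 or 4 give 7 or 42 days, and study day holds whenever the start date is known.
- **Safety tables.** A reader might also infer that Table 3 removes adverse events occurring after the last visit, while the subject still holds drug. It does not. SAP 4.4.1 excludes them by ending on-study events at the last study visit, so a last-contact cut-off in Table 3 would conflict with that section.
- **Concomitant medications.** Overlap with treatment is a problem only for the inverted interval, and a medication with no onset date is deemed concomitant under Table 7.
- **The day-before convention has a source.** The Protocol Synopsis describes dosing through the morning before Visit 5, and Protocol 7.1 has open-label dosing end the evening before Visit 8. That supports the completer bullets, which are not challenged here. It does not carry over to Visits 3 and 4, where treatment is meant to continue and a dose is given on site.
- **A missing first-dose date is unlikely.** Staff query dosing at Visit 3 and data are cleaned before analysis. This bears on frequency; it does not supply a rule for the subject in whom the date stays missing. Note 2 also usefully stops an open-label end date being assigned to someone who never entered open label, and that function should be kept.

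**Conclusion.** The point holds in this limited form. In case (a), exposure is 0 days when the last visit is Visit 2, or Visit 5 for the open-label period, and one day short when it is Visit 3 or 4. In case (b), a dosed subject has no exposure, treatment-emergent window or study day and drops out of the MMRM although in the FAS.

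The documents give no frequency. As assumptions only: if 1% to 3% of 430 subjects were lost without an Exit Visit, that is 0.01 × 430 = 4.3 to 0.03 × 430 = 12.9 subjects. This is a ceiling for case (a), since the last-dose date must also be missing, and only some would be inverted rather than one day short. If 0% to 1% lacked a first-dose date, case (b) covers 0 to 4.3 subjects. The primary conclusion is unlikely to turn on either. The change is still worth making, because stated rules produce wrong derived dates and the correction is simple.

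**What to change.** In SAP Table 3:

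1. For a non-completer with no Exit Visit and no last-dose date, set the end date to the last available visit date, never earlier than that period's treatment start date.
2. If dosing is documented but the first-dose date is missing, impute the start as the Visit 2 date (double-masked) or the Visit 5 date (open label). SAP 7.6 already uses the date of first dispensation in the same way for compliance.
3. Limit Note 2 to subjects who took no dose in the period concerned.

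Leave the treatment-emergent definition in SAP 4.4.1 as it is.

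The cost is a few lines of SAP text and derivation code. Exposure may be overstated by about a day in some subjects, for example one last seen at Visit 6, where no dose is given in clinic and that evening's dose is unknown. For a former timolol-arm subject last seen at Visit 5, the subtraction in SAP 7.7 becomes 91 − 90 = 1 or 91 − 91 = 0. The second result arises because Visit 5 can count as a timolol day, which is a property of that subtraction and not of Table 3.
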